# I. BACKGROUND AND PUBLIC HEALTH IMPLICATIONS

#### A. SPONTANEOUS ABORTION

Spontaneous abortion (SAB) is one of the most common complications of pregnancy, resulting in fetal loss prior to 20 weeks of gestational age. Between 12% to 15% of clinically recognized pregnancies result in a SAB, with the vast majority occurring prior to 12 weeks gestation. When including clinically unrecognized pregnancies, the pregnancy loss rate is substantially higher, with one carefully conducted study including such pregnancies finding a loss rate of approximately 30% following implantation.

Chromosomal anomalies are implicated in approximately half of all SABs, with a higher incidence of abnormal fetal karyotype at earlier gestational ages; an additional unknown proportion of SABs is due to genetic abnormalities undetected by standard karyotype analysis. The etiology of SAB in apparently healthy women with chromosomally and structurally normal fetuses is unknown. One of the most important risk factors is age, with rates increasing with maternal age (9% at age 22, 20% at age 35, 55% at age 42, and 84% at age 48 years and above). Other factors associated with SAB include smoking, alcohol, asthma, parity, prior history of SAB, diabetes, febrile illness, and obesity.

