# F. IDENTIFYING POTENTIAL CASES AND CONTROLS IN CLAIMS-BASED AND ADMINISTRATIVE DATA (PHASE 1)

#### 1. Cases

The inclusion criteria for cases and controls are summarized in Appendix 1. Using claims and administrative data, women who have experienced a SAB will be initially identified using the codes in Appendix 2 occurring in the inpatient, emergency department, or ambulatory care setting. To avoid including follow-up visits, a 98-day (i.e., 14 week) washout period will be used to identify incident SAB events. If there are multiple incident SAB events for a given patient, we will select the first chronological event in the study period. Though the average gestational length of pregnancies ending in miscarriage is shorter (i.e., 10 weeks), we chose the 14-week washout period to enhance the specificity for detecting incident SAB events. Initially, inclusion based on period of enrollment will be conducted through the use of administrative and claims-based data; women whose pregnancies have ended in a SAB will only be considered a potential case if based on claims-based and administrative data, they are enrolled continuously for the 244 days prior to their medical encounter for SAB. The 244-day pre-SAB enrollment criterion for potential cases incorporates a 90-day period prior to pregnancy start, 140-day period for the maximum gestational length for a pregnancy ending in SAB, and a 14-day period to allow for delays in seeking medical attention for SAB.

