#### 2. Controls

We will identify live deliveries in claims-based and administrative data using codes in Appendix 3. To avoid including post-partum care visits, we will use a washout period of 270 days to define an incident delivery. For women who have both a SAB and live delivery during the study period, the SAB will be retained, while the live delivery will be discarded; this will be done to retain the SAB in instances where multiple pregnancies result in one or more miscarriages, and the remaining fetus(es) results in a live delivery. Initially, inclusion based on period of enrollment will be conducted with administrative and claims-based data; women whose pregnancies have ended in a delivery will only be considered for inclusion as a potential control if based on claims-based and administrative data, they are enrolled continuously for the 360 days prior to delivery hospitalization. The 360-day pre-delivery enrollment criterion for potential controls incorporates a 90-day period prior to pregnancy start and a 270-day period, the average length of term pregnancy. After chart review is conducted, we will ensure that controls are enrolled for a minimum of 90 days prior to pregnancy start through the index event date in

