#### H. MATCHING POTENTIAL CONTROLS TO CHART-CONFIRMED CASES (PHASE 3)

After chart review of potential cases, we will identify 1 or more potential controls (up to a maximum of 6 controls) for every case to pursue medical charts. Controls will be matched to cases on Data Partner, age, and pregnancy start (+/- 14 days), with pregnancy start estimated initially in electronic data and chart-confirmed at a later stage. Matching on pregnancy start will address temporal trends in exposure by gestational age and calendar time by maximizing the comparability between cases and controls with respect to the gestational and calendar periods covered by the risk and control intervals. Furthermore, matching on Data Partner and, maternal age will address confounding, which might occur if these factors are associated both with SAB and with timing of vaccination. If sufficient controls are available, we will also attempt to match on other important confounding factors, including comorbidities and infections, further described later in the protocol. Conditional logistic regression will be used to account for the matching and to allow for a different underlying time trend in exposure for each case:control set, which addresses the possibility of effect modification of the exposure-period association by confounders matched upon.

The matching criteria are described in more details as follows. We will match cases to controls on pregnancy start, Data Partner, and maternal age within +/-18 months. Among potential controls, we will initially estimate pregnancy start date based on an algorithm that utilizes electronic data and that is further described in the PRISM Influenza Vaccines and Birth Outcomes Protocol. Because birth certificate data and infant claims-based codes for gestational age provide more precise estimates of gestational age than their maternal claims-based counterparts, we will link potential controls identified in Data Partner records to infant Data Partner records and/or birth certificate data. We will use claims-based codes for gestational age for infants born preterm, post-term, or after a prolonged gestation (Appendix 4). If claims-based codes for gestational age for gestational age for infants age for infants in Appendix 4 are not evident, we will assume a gestational length of 270 days.

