If there are sufficient control numbers, we will consider matching controls to cases on diagnoses of diabetes, obesity, asthma, and multiparity based on CPT and ICD9-coded data. Finally, where information on particular time-varying confounders is available in claims-based data, we will attempt to match cases and controls on such factors if sufficient controls exist. We will attempt to match cases and controls on the presence of urinary tract infections, respiratory infections, gastrointestinal infections, sexually transmitted infections, and medically attended fever within a 1-28 day period prior to SAB/index date, identified using ICD9-coded data (Appendix 5). Finally, we will collect information from the medical record on factors not matched upon in the design phase, such as smoking, alcohol, and substance abuse, and adjust for them in regression models if feasible.

Multiparity will be identified using codes listed in Appendix 5. The algorithms for identifying obesity and diabetes are described in the PRISM Influenza Vaccines and Birth Outcomes Protocol. Asthma will be identified using an algorithm validated and developed by the Medication Exposure in Pregnancy Risk Evaluation Program (MEPREP), an FDA-sponsored collaboration between 11 health plans. To be considered asthmatic, a woman must have one of the following during the 90 days prior to pregnancy through end of pregnancy: (1)>=2 outpatient visits at least 30 days apart with ICD9 diagnosis code 493\*, (2) >=1 inpatient visit with ICD9 diagnosis code 493\*, or (3) >=1 outpatient visit with ICD9 diagnosis code 493\* and >=1 dispensing of an asthma medication (short- or long-acting beta-agonist, inhaled corticosteroid, leukotriene receptor antagonist, mast cell stabilizer, methylxanthine). This algorithm was shown to have a positive-predictive value of 95% in MEPREP.

Among potential controls meeting matching and enrollment criteria, TIV identified in claims or IIS data must be received between -6 weeks gestation and 2 weeks past the case's gestational age at SAB, with gestational age estimates from birth certificate or infant-claims based estimates. A 2-week margin before and after the gestational period of interest will be initially incorporated to allow for misclassification of gestational age in live delivery controls due to use of claims and birth certificate data for gestational age estimates.

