In Primary Objective 3, we will determine the accuracy of claims data for matching potential cases and controls on potential confounders. We will determine the positive predictive value in cases and controls for each of the confounders matched upon. We will also determine the proportion of matched case-control pairs that have concordant status in chart data for each matching factor (i.e., confounder).

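### The claims window for asthma closes at the end of pregnancy, so a term control has about 360 days to qualify and an average SAB case about 160

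*Protocol*

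**What the plan says.** Protocol section III.H gives the claims definition of asthma that would be used for matching: "a woman must have one of the following during the 90 days prior to pregnancy through end of pregnancy". Three alternatives follow, any one of which is enough. The first is at least "2 outpatient visits at least 30 days apart with ICD9 diagnosis code 493". The second is one inpatient visit with that code. The third is one outpatient visit with that code plus one dispensing of an asthma drug. No separate closing date is given for controls.

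The lengths of the two kinds of pregnancy are stated elsewhere:

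- Section III.F.1 puts the average pregnancy ending in miscarriage at 10 weeks and the maximum at 140 days. Section I.A describes SABs "with the vast majority occurring prior to 12 weeks gestation". Section III.O drops SABs before 6 weeks.
- Section III.F.2 explains that the control's initial enrollment requirement "incorporates a 90-day period prior to pregnancy start and a 270-day period, the average length of term pregnancy". Section III.H adds that, where no gestational-age code is found, "we will assume a gestational length of 270 days".

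Matching on asthma is to be considered only if there are enough controls (sections III.H, III.K and V.B). For any confounder matched on, section IV.A plans the positive predictive value (PPV) in cases and in controls, and "the proportion of matched case-control pairs that have concordant status in chart data for each matching factor".

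**The concern.** A matching factor should be measured over the same time in both members of a pair. Here the closing event is the outcome itself: the SAB shortens the case's window, while the control's window runs on to delivery. The extra control time also lies after the index date, when the case no longer contributes anything.

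The protocol avoids this for its other time-bound items. Section III.H counts infections and fever in the 28 days before the SAB or index date, and section III.I ends the control's final enrollment requirement at the index date. Asthma departs from that convention.

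Two things are at stake if asthma is matched on. First, a woman coded negative is more likely to be an unrecognised asthmatic if she is a case than if she is a control, so the pairs are less alike than the matching implies. Section I.A lists asthma among the factors associated with SAB. Second, Objective 3 is a primary objective about how well claims serve for matching on confounders. Unequal windows would add disagreement with the charts that comes from the rule and not from the claims.

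**Working it through.** **Inputs from the protocol.** Look-back before pregnancy start, 90 days; term pregnancy, 270 days; SAB gestation g with mean 70 days (10 weeks), kept range 42 days (6 weeks) to 140 days (20 weeks).

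**The plan's own figure.** Control look-back = 90 + 270 = 360 days, which reproduces the 360 days in section III.F.2. Because that section requires enrollment over those 360 days, the longer control window is observed time.

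**Case window and ratio.** Case window = 90 + g; ratio = 360 / (90 + g).

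| SAB at | Case window (days) | Ratio |
|---|---|---|
| 6 weeks | 132 | 2.73 |
| 8 weeks | 146 | 2.47 |
| 10 weeks (mean) | 160 | 2.25 |
| 12 weeks | 174 | 2.07 |
| 16 weeks | 202 | 1.78 |
| 20 weeks | 230 | 1.57 |

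The ratio exceeds 2 when 90 + g < 180, that is g < 90 days or about 12.9 weeks. For a 10-week SAB, 270 − 70 = 200 of the control's 360 days fall after the index date.

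**Other delivery dates.** Against a 10-week SAB, a control delivered at 245 days gives (90 + 245)/160 = 2.09, and one at 294 days gives (90 + 294)/160 = 2.40. The shortest delivery gestation in Appendix 4 is 168 days, above the 140-day maximum for a SAB, so the direction never reverses.

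**What this does to sensitivity (illustration).** The protocol gives no visit or dispensing rates, so these are assumed. For a true asthmatic, coded visits and dispensings were simulated as Poisson processes, and she was flagged if she met the first or the third criterion (inpatient visits were not modelled). The last two columns assume 8% asthma prevalence in both groups and give the share of true asthmatics among women coded negative: 0.08(1 − s) / [0.08(1 − s) + 0.92], where s is sensitivity.

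| Visits / dispensings per year | s, 160 days (case) | s, 360 days (control) | Asthma among coded-negative cases | Among coded-negative controls |
|---|---|---|---|---|
| 1 / 2 | 0.23 | 0.57 | 6.3% | 3.6% |
| 2 / 4 | 0.51 | 0.86 | 4.1% | 1.2% |
| 4 / 6 | 0.80 | 0.98 | 1.7% | 0.2% |

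For the middle row: cases 0.08 × 0.488 / (0.08 × 0.488 + 0.92) = 4.1%; controls 0.08 × 0.143 / (0.08 × 0.143 + 0.92) = 1.2%.

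**First criterion alone.** P = 1 − e^(−m)(1 + m), with m = yearly rate × (window − 30)/365. At 2 visits a year, m = 0.71 for cases and 1.81 for controls, giving 16% against 54%. This is a wider gap than the algorithm as a whole shows, because the third criterion recovers many women.

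**After the change.** Both windows are 90 + g days: 160 and 160 at 10 weeks, 230 and 230 at 20 weeks, ratio 1.00.

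**The case against.** The best defence is that this is one optional variable in a feasibility study. Data Partner, maternal age and pregnancy start, the factors always matched on, are untouched, and the odds ratio is a pilot objective. That stands, and it limits how much the point matters.

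Several stronger readings are tempting, and the documents do not support them:

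- **Most asthmatic cases would be coded non-asthmatic.** This follows from the two-visit criterion at low visit rates. Over the two criteria simulated, sensitivity in cases is 51% at 2 visits and 4 dispensings a year and 80% at 4 and 6. It falls well below half only at the lowest rates in the table.
- **Matching fails and the odds ratio is biased.** Asthmatics who are flagged are still matched, so what remains is residual imbalance. Everyone is vaccinated, so bias also needs asthma to be related to when the vaccine was given. The protocol names that mechanism in general terms (sections III.A and V.B) but gives no figure for asthma.
- **Objective 3 would blame claims quality.** Section IV.A does not say how discordance will be attributed. Chart asthma is collected (section III.O), so pair concordance could expose part of the problem. PPV by case status would largely miss it, because a shorter window mainly lowers sensitivity.
- **Diabetes, obesity and multiparity share the flaw.** The first two algorithms sit in another protocol, and no window is stated for multiparity. Nothing is shown for these three.
- **The censoring in Figures 2 to 5 already settles it.** Those captions describe vaccine risk and control intervals, not the look-back for comorbidities.

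The protocol also cites a 95% PPV for the algorithm. That says nothing about sensitivity, so it does not answer the point.

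**Conclusion.** The defect is real and limited. As written, the asthma rule gives a term control 2.25 times the window of an average SAB case and uses claims from after the index date. The control's window is longer at every eligible SAB gestation. This part rests only on the protocol's figures.

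If asthma is matched on, sensitivity will be lower in cases than in controls. The range from 23% against 57% to 80% against 98% rests on assumed Poisson rates and a 10-week SAB; the direction does not depend on the rates. The result is more hidden asthma among coded-negative cases than among their matched controls, and extra chart discordance in Objective 3. Whether the pilot odds ratio is biased, and by how much, cannot be derived from the protocol.

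**What to change.** In section III.H, let the asthma window run from 90 days before pregnancy start through the SAB date in cases and the index date in controls. Use the same window when asthma is assessed for Objective 3, so that claims and chart are compared over the same period in both groups.

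The cost is one phrase and one date variable. The date is available at the matching step: cases are chart-confirmed by then, and the vaccination screen for potential controls already uses the case's gestational age at SAB.

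There are two small downsides. Fewer controls will be flagged as asthmatic, which is what equal ascertainment implies. The cited 95% PPV may not carry over exactly to the shorter window, and the text should say so.

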#### I. IDENTIFYING POTENTIAL CONTROLS IN CLAIMS-BASED AND ADMINISTRATIVE DATA (PHASE 3 AND 4)

After 2 or more potential controls are identified in electronic data for each chart confirmed case, we will then conduct a second round of chart review to confirm that these controls have vaccine exposure in the gestational period of interest (i.e., 4 weeks before pregnancy start to the index date). These potential controls will proceed to full chart review to confirm live delivery, gestational age at delivery, pregnancy start date, TIV exposure, and gestational age at vaccination. Controls will only be retained if they received TIV between -4 weeks gestation and the index date. Initially we will require controls to be continuously enrolled in the 360 days prior to delivery. This 360-day period incorporates a 90-day period prior to pregnancy start and a 270-day period, the average gestational length of a term pregnancy. Following chart review, controls will only be retained if they are determined to have enrollment 90 days prior to pregnancy start through the index date. Following chart review, if both controls in a given case-control set do not meet inclusion criteria, we will attempt to match the case to an unmatched control from a different case-control set, if available. If cases remain unmatched despite these attempts, they will only be included in analyses for Objectives 1 and 2. If both controls in a given case-control set meet inclusion criteria, we will randomly select one control.

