#### K. CASE-TIME-CONTROL DESIGN

As proof-of-concept, a case-time-control study design will be implemented to examine whether risk of SAB is elevated in specific time periods following TIV or in specific gestational periods following TIV. We will identify SAB cases that were vaccinated between -4 weeks gestation until the date of the SAB. Since the likelihood of receiving TIV differs by gestational age and calendar time, we will match each case to a vaccinated control based on Data Partner, maternal age, and pregnancy start, where the control must have received TIV between -4 weeks gestation and the case's gestational age at SAB. In order to understand the feasibility of using the case-time-control design in Mini-Sentinel, we will first examine (1) the validity of claims data for identifying SAB; (2) the validity of birth certificate and claims data for identifying start among live delivery controls for matching them to chart-confirmed cases; and (3) the validity of using claims data for matching cases to controls on confounders, if matching on factors other than DP and pregnancy start is ultimately implemented. The details of the descriptive statistics for Primary Objectives 1-3, which will be used to address each of these aims, are described further in the analytic section of the protocol.

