In Pilot Objectives 4-5, we will implement the case-time-control design and analyze the resulting data. For Pilot Objective 4, we will define the risk interval as receipt of TIV within 1-28 days prior to SAB, while the control interval will be defined as receipt of TIV outside of the risk interval (i.e., between -4 weeks gestation and 29 days prior to SAB, Figure 2). Although we will strive for an exact match by pregnancy start, it is plausible that we will not identify enough controls to match to cases. If an exact pregnancy start match is not possible, we will assign an index date in controls that corresponds to the gestational age at SAB in the case. Of note, cases and controls will only be informative if vaccinated in either the risk or the control interval. In exploratory analysis, we will stratify the analysis for this objective by gestational age at SAB (less than 12 weeks gestation vs. 12 or more weeks gestation) since the etiology of SAB differs by gestational age at occurrence. In addition, because the underlying causes of SAB may differ by whether a heartbeat is detected prior to the miscarriage, we will consider stratifying by this factor, depending on whether we have sufficient case numbers. If we have sufficient case numbers, we will also consider excluding cases that have a threatened abortion identified prior to vaccination.

**Figure 2:** Example case and control for case-time-control design with the risk interval defined as 1-28 days before SAB, and the control interval design defined as -4 weeks gestation through 29 days before SAB. Follow-up time after the SAB and index dates will be censored.

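### The rule for borrowing a control from another set ignores the donor set's SAB gestation, so a control from an earlier-SAB set brings a truncated vaccination window (pilot objectives only; cheap fix)

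*Protocol*

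**What the plan says.** The case-time-control comparison depends on case and control having the same opportunity for vaccination. Protocol III.K states the condition for the matched control: "where the control must have received TIV between -4 weeks gestation and the case's gestational age at SAB".

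Controls reach that point in two steps, both tied to the case they were drawn for:

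- **Electronic sampling (III.H):** "TIV identified in claims or IIS data must be received between -6 weeks gestation and 2 weeks past the case's gestational age at SAB".
- **Chart retention (III.I):** "Controls will only be retained if they received TIV between -4 weeks gestation and the index date". The index date is the one set by that case.

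III.I also creates spare controls: "If both controls in a given case-control set meet inclusion criteria, we will randomly select one control". The other valid control is left over. For a case that loses both of its controls, the same paragraph says "we will attempt to match the case to an unmatched control from a different case-control set, if available". A case that still has no match is used for Objectives 1 and 2 only.

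For the analysis, III.K gives the Objective 4 exposure: "we will define the risk interval as receipt of TIV within 1-28 days prior to SAB". Where pregnancy starts differ, "we will assign an index date in controls that corresponds to the gestational age at SAB in the case". A borrowed control is therefore classified against the recipient's SAB gestation, not the donor's.

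**The concern.** A spare control has already been filtered on vaccination by another woman's SAB gestation. If that gestation is earlier than the recipient's, the last part of the recipient's window is empty for her by construction. That last part is where the 1-28 day risk interval lies.

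The existing rules do not catch this. The requirement that vaccination precede the recipient's SAB removes unsuitable spares from later-SAB sets, but every spare retained for an earlier SAB passes it automatically. The listed matching factors (Data Partner, age, pregnancy start) do not involve SAB gestation.

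In the affected pairs a vaccine with no effect would not give an odds ratio of 1 for Objectives 4-5. The scan p-values in IV.C are also affected. They come from randomly swapping the two vaccination times within a pair, which assumes the times are interchangeable, and in these pairs they are not.

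**Working it through.** The plan gives no figure for this point, so there is none to reproduce.

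**Inputs from the protocol.** Window from -4 weeks to SAB gestation (III.K); Objective 4 risk interval of 28 days, i.e. 4 weeks, before SAB (III.K); SABs before 6 weeks excluded (III.O); target of 100 pairs (III.E, V.B).

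**Assumptions not in the protocol.** Vaccination timing uniform over the window; the donor is a spare who was retained in her own set. Let g2 be the recipient's SAB gestation and g1 the donor case's, in weeks.

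**Step 1. Objective 4, one pair.**
- Properly sampled control: 4 / (g2 + 4).
- Spare with g1 < g2: max(0, g1 - (g2 - 4)) / (g1 + 4).

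With g2 = 12 the proper value is 4/16 = 25.0%.

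| Donor SAB (g1) | Chance in risk interval | Ratio to 25% |
|---|---|---|
| 11 | 3/15 = 20.0% | 0.80 |
| 10 | 2/14 = 14.3% | 0.57 |
| 9 | 1/13 = 7.7% | 0.31 |
| 8 | 0/12 = 0% | 0 |

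At a gap of 4 weeks or more the zero follows from the windows alone and needs no uniform assumption. A spare from a set with g1 at or above g2, screened for vaccination by g2, has the proper chance.

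**Step 2. Objective 5, g2 = 12 and g1 = 8.** Intervals in completed weeks, so -4 to 5, 2 to 7 and 6 to 12 on a continuous scale.

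| Interval | Proper control | Spare | Effect on OR |
|---|---|---|---|
| -4 to 4 | 9/16 = 56.2% | 9/12 = 75.0% | down |
| 2 to 6 | 5/16 = 31.2% | 5/12 = 41.7% | down |
| 6 to 11 | 6/16 = 37.5% | 2/12 = 16.7% | up |

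The last two directions hold on average, not for every pair. With g1 = 12 and g2 = 16, the 6-11 week chance is 6/16 = 37.5% for the spare against 6/20 = 30.0%. With g1 = 6 and g2 = 7, the 2-6 week chance is 4/10 = 40.0% against 5/11 = 45.5%.

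**Step 3. Objective 4 odds ratio under no effect.** For each set let c be the case's chance of falling in the risk interval, and x the control's: c for an ordinary control, the Step 1 value for a borrowed one. The matched OR is the sum of c(1 - x) divided by the sum of (1 - c)x. Two SAB-gestation distributions were assumed: uniform over 6-20 weeks, and early-weighted with mean 10.4 weeks. Donors were drawn at random among those vaccinated by g2.

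| Share of sets rescued | Early-weighted | Uniform |
|---|---|---|
| 4% | 1.01 | 1.02 |
| 9% | 1.04 | 1.04 |
| 16% | 1.06 | 1.08 |
| 25% | 1.10 | 1.12 |

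A 5% share therefore corresponds to about 1.02-1.03 and a 20% share to about 1.07-1.09, with the uniform case at the top of that range, close to 1.10. Within rescued sets alone the OR is about 1.4-1.7 depending on the assumed distribution. It is about 2.4-4.0 where the donor's SAB was earlier and 1.00 where it was the same or later.

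**Step 4. Scale against sampling error.** With 100 pairs and exposure of 25-30%, the number of discordant pairs is 100 × 2 × 0.25 × 0.75 = 37.5 to 100 × 2 × 0.30 × 0.70 = 42. The standard error of the log OR is 2/√37.5 = 0.33 to 2/√42 = 0.31. A pooled OR of 1.03 is a shift of ln 1.03 = 0.030, about 0.1 standard errors. At 1.09 it is 0.086, just under 0.3.

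**The case against.** Four points on the other side deserve weight.

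**Few sets will be rescued.** Borrowing is only attempted where a control is available, and she must fit on Data Partner, age within 18 months and pregnancy start within 14 days. The population is two Data Partners, two seasons and ages 18-34. If each of two controls fails independently with probability 0.2 to 0.5 (assumed), 0.2² = 4% to 0.5² = 25% of cases lose both. Under further assumptions about the spread of ages and pregnancy starts, only about 1 to 5 cases in 100 would find an eligible spare, and about 0.4 to 3 of those spares would come from an earlier-SAB set. On those assumptions the 20% scenario is not reached. None of these inputs is in the protocol, so this lowers the likely size without settling it.

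**Only pilot work is affected.** Objectives 4-8 are proof of concept, V.B concedes limited power, and the scans are called exploratory. Primary Objectives 1-3 are untouched. This stands and governs the severity.

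**The effect on an earlier-SAB donor can be overstated.** A reader might infer that any such donor has almost no chance of vaccination in the recipient's risk interval. That holds only at gaps of about 3 weeks or more; at 1 to 2 weeks she keeps roughly 55-80% of the proper chance. A reader might also infer that the rule always pushes toward a false harm signal. It does so for Objective 4, but the -4 to 4 and 2 to 6 week intervals move the other way.

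**The term unmatched control is open.** It could also cover a control rejected by her own set for vaccination after its index date. A reader might conclude that she is then certain to fall in the recipient's risk interval. With SABs at 8 and 12 weeks and vaccination in weeks 8-10 she would. With SABs at 8 and 14 weeks the risk interval is weeks 10-14 and she would not. The two-week sampling margin also applies to electronic dates, so it does not fix her chart-dated vaccination. This reading is not quantified here.

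What the objection does not supply is any protocol text that corrects the truncation for a spare from an earlier-SAB set.

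**Conclusion.** The point holds as a minor flaw in the fallback matching rule. As written, a borrowed control from an earlier-SAB set has a vaccination window cut at another case's SAB gestation. In those pairs Objectives 4-5 are biased under no effect, and the exchangeability behind the scan p-values fails. The existence of the problem does not depend on uniform timing: at gaps of 4 weeks or more a retained spare cannot be in the 1-28 day interval at all. Its size does depend on uniform timing, the assumed SAB-gestation distribution, random choice of donor, and the unstated share of rescued sets.

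The documents do not support a claim that the pilot results as a whole are invalid. Interchangeability fails only in the rescued pairs with an earlier-SAB donor, and the pooled shift is small beside the sampling error of a study that V.B describes as having about 80% power for a relative risk of 2.4. The reason to act is that the protocol tests this design for later use, and the correction is nearly free.

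**What to change.** Add one sentence to the borrowing rule in III.I: a case may take a control from another set only if that control meets the existing matching criteria, was vaccinated by the recipient case's SAB gestation, and comes from a set whose case had an SAB gestation the same as or later than the recipient's. The second condition restates what III.K already requires; the third is new and also settles which spares are eligible. Failing that, draw a new control from the electronic pool against the recipient's own window, or leave the case unmatched as III.I already allows.

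Under the assumptions above, borrowing from same-or-later sets gives a null odds ratio of 1.00 for Objective 4. The cost is that some rescue matches are lost (about half if donors are random), so a few more cases contribute only to Objectives 1 and 2.
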